## 5. TREATMENT PLAN AND STUDY SCHEMA

### 5.1 Study Design

This is a single-arm open-label phase Ib/II clinical study assessing the efficacy of concurrent high dose ascorbate in combination with radiotherapy in patients with locally advanced, resectable, high grade sarcomas, as measured by pathological response rates. Patients will be treated with three times weekly IV ascorbate concurrently with radiation therapy. Surgery will be performed 4-6 weeks from the end of radiation therapy to allow for resolution of acute toxicities per current standard of care.

### 5.2 Phase Ib

The phase Ib portion of this study is to ensure the safety and tolerability of high dose ascorbate in combination with EBRT as assessed by incidence of dose-limiting toxicities (DLT). Although this combination has been shown to be safe and well tolerated in GBM, this combination has not been studied in sarcoma patients. EBRT will be given at the standard dose for resectable soft tissue sarcomas according to the NCCN sarcoma guidelines. Patients will receive 50 Gy over 25 fractions for extremity and trunk sarcomas or 45 – 50.4 Gy in 28 fractions for retroperitoneal sarcomas, during which time they will be receiving three times a week IV high dose ascorbate. IV ascorbate infusions will be continued until the end of radiation therapy. Surgery will be performed 4-6 weeks from the end of radiation to allow for adequate tissue healing and resolution of acute toxicities.

Ascorbate will be dosed at an initial dose of 75gm IV three times a week concurrently with radiation therapy provided patient tolerated the test dose of ascorbate during screening without any reactions. Initially 3 patients will be entered at the Dose 0 for ascorbate and be monitored at this three times a week dose until surgery when safety issues will be addressed. Otherwise, ascorbate dose will be deescalated and dose -1 will be explored as outlined. For this protocol DLT will be defined as an attributed adverse event (definite, probable or possible) that meets the criteria (Section 6.3).

**Table 1. Phase 1b Dose De-escalation Schedule**

Number of Patients with DLT at a Given Ascorbate Dose	Decision Rule
$\geq 2$	Dose level will be declared toxic. If this is the lowest dose level, stop the study due to excessive toxicity; otherwise enter three additional patients at the next lowest dose level.
$\leq 1$ out of 3	Enter three more patients at this dose level.
$\leq 1$ out of 6	This is the recommended dose for the subsequent Phase2.

## Ascorbate Dose Levels

[figure not shown]
Dose 0      Ascorbate 75 gm IV three times weekly concurrently with radiation  
Dose -1      Ascorbate 62.5 gm IV three times weekly concurrently with radiation  
•      Initial dose for all = Ascorbate 75gm IV

## 5.3 Phase 2

[figure not shown]
The phase 2 part of the study will provide an estimate of the relative treatment effect of pharmacological ascorbate in combination with preoperative EBRT in subjects with locally advanced, resectable, extremity or retroperitoneal high grade sarcomas, as measured by pathological response rates.

As above, patients will receive the first dose of pharmacological ascorbate intravenously on day 1 of week 1 provided no reactions are seen to the test dose. This will be followed by 3 times a week dosing (= 15 doses total) at Dose 0 until completion of EBRT. Standard doses of radiation for resectable soft tissue sarcomas according to the NCCN sarcoma guidelines will be administered. Patients will receive preoperative radiation at a dose of 50 Gy over 25 fractions for extremity and trunk sarcoma or 45 to 50.4 Gy in 28 fractions for retroperitoneal sarcomas starting on week 1 day 1. Subjects should be followed either by clinic visit or phone contact every 12 weeks (+/- 4 weeks) for approximately 24 months after the end of the treatment phase, at which time the initial survival data and disease recurrence will be assessed. Details as per study calendar (Section 10).

[figure not shown]

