## 5.6 Concomitant Ascorbate (High-dose Ascorbic Acid) Infusions

5.6.1 **Participant dose.** All patients will receive a standard ascorbate dose of 75 gm given over 120 minutes

5.6.2 **Administration.** Based on subject tolerance; infusion rate should not exceed 500 mL/hour without consulting with physician. Recommended infusions times are as follows (Table 1) but may be adjusted for subject comfort. Changes in infusion rates should be recorded.

5.6.3 **Initiation.** Start the week prior to chemoradiation with one 15-g infusion. This is the test dose. 75 gm dosing begins week 1 of radiation therapy. If the participant fails the 15g test dose it is not considered dose limiting toxicity.

5.6.4 **Schedule.** Scheduled three times weekly during chemoradiation;

5.6.5 **Duration.** Subjects will continue with therapy until the end of standard radiation therapy or if any criteria of removal are met (Section 5.7)

5.6.6 **Dose modifications.** Provided in Section 6.2

**Table 1.** Recommended Infusion Times for Pharmacological Ascorbate †

Ascorbate dose (500 mg / mL)	Total volume*	Osmolarity (mOsm/L) §	Infusion Time
15g (30 mL)	250 mL	681	30 minutes
75g (150 mL)	1000 mL	851.7	120 minutes
62.5 g (125 mL)	1000 mL	709	120 mins

† Provided by Drug Information Center at the University of Iowa, July 2011

\* Sterile water for injection only. Do not use D5W

§ Theoretical calculations provided by Drug Information Center; targeted osmolarity range is 500 – 900 mOsm/L

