## 5.7 Radiation therapy

External beam radiation therapy will be given at the standard dose for resectable soft tissue sarcomas according to the NCCN sarcoma guidelines. Patients with extremity and trunk STS will receive 50 Gy over 25 fractions and those with retroperitoneal STS will receive 45 to 50.4 Gy in 28 fractions, during which time they will be receiving three times weekly IV ascorbate until the end of radiation therapy. Surgery will be performed 4-6 weeks from the end of radiation to allow for adequate tissue healing and resolution of acute toxicities.

Radiation therapy for this protocol is as per currently used standard pre-operative radiation therapy at the University of Iowa even for non-protocol patients. Selected guidelines from previously conducted Radiation Therapy Oncology Groups (RTOG) studies are briefly summarized for this protocol.

- 5.7.1 **Preoperative Radiation therapy (3D-CRT or IMRT).** Either 3D conformal radiotherapy or intensity modulated radiation therapy may be utilized for adequate tumor coverage and to meet the dose constraints for critical normal structures.
- 5.7.2 **Radiation treatment planning scans and immobilization.** CT scans with patient in a stable and comfortable position will be used for planning. MRI scans are optional and may be used for co-registration with CT for tumor localization as needed. VacLoc or other immobilization devices can be used for immobilization.
- 5.7.3 **Target volumes and treatment field (Extremity Sarcoma):**

**Gross Target Volume (GTV):** Outline of the tumor as seen on CT or CT/MRI fusion.

**Clinical Target Volume (CTV):** CTV = GTV plus 4 cm margins in the proximal and distal directions. However, the margin can be reduced if it extends beyond the compartment, the field can be shortened to include the end of a compartment. The radial margin from the lesion should be 1 cm. It can be reduced in areas confined by the fascial barrier or bone or skin surface as per standard of care and treating radiation oncologist's discretion.

**Planning Target Volume (PTV):** Include CTV and error of setup and organ motion. Typically PTV includes CTV plus 0.5 - 1 cm in all dimensions. Final PTV is usually GTV + 5 cm longitudinal and 2 cm radial, except where restricted by the compartment end, fascia, bone or skin surface as per standard of care and treating radiation oncologist's discretion.

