### 9.4 Ascorbate levels

Serum ascorbate levels will be drawn at screening, 30 mins post at week 1 day 1, as well as 30 mins post week 3 Day 1 and 30 min post last infusion in week 5. This is being done to ensure a target serum level of 20 mM is reached during treatment.

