## 10. STUDY CALENDAR

### 10.1 Study Procedures

	Screen b	Treatment a					Off treatment and end of study c	Follow Up d
		Week 1	Week 2	Week 3	Week 4	Week 5 (+1wk j )		
H & P	X	X		X		X		
Tumor biopsy (optional)	X b							
Performance status	X						X	X
Clinical MRI/ Staging CT	X						X	X e
Pregnancy test k (urine)	X							
G6PD	X							
EKG	X							
CBC w/diff	X			X		X		
PT/INR, PTT & uric acid	X							
Height	X							
Weight, BSA	X						X	
Vitals (BP, pulse) m	X	X	x	X	x	X	X	
Comprehensive metabolic panel (CMP)	X	X		X		X	X	
Ascorbate infusion	X i	XXX	XXX	XXX	XXX	XXX		
Blood for ascorbate levels f	X	X		X		X		
ROS Research blood g	X	X		X		X	X	
Immunology research lab g	X					X	X	
Iron Panel including ferritin h	X						X	
T2* /QSM and DWI MR imaging sequences (optional)	X			X			X	
Adverse Events & Con Meds			X	X	X	X	X	

**a** study day 1 is defined as radiation therapy day 1 (i.e., fraction 1).

**b** screening labs, history, and physical must be obtained  $\leq$  28d from d1. G6PD may be obtained at any time prior to test dose. MRI/CT obtained  $\leq$  28d from d1 (RT sim is acceptable). Pregnancy test per institutional guidelines. Optional tumor biopsy can be done anytime before week 1 dosing.

**c** includes both off-treatment evaluation and study completion. Study completion requires a final study dictated visit 4 to 6 weeks after the last dose of ascorbate. Follow at least monthly until resolution of all ascorbate related adverse events.

**d** approx every 3 months (every 12 weeks [+/- 4 weeks]) for overall survival through passive chart review, phone call or scheduled follow-up visit for 2 years

**e** Imaging as per standard of care for site specific sarcomas

**f** 4cc green-top Na-Heparin tube. Draw pre-infusion at 15g dose, then 30 min post-infusion: week 1 day 1 , week 3 and last infusion of week 5

**g** 6cc pink-top EDTA tube. Draw pre infusion The specimen should be placed on ice immediately after draw and carried to the lab

**h** At time of screening and end of study

**i** Test dose of 15 g intravenously once G6PD levels confirmed to be adequate. A physician must review the patient's medication list against the list of medications prohibited on this trial prior to the test dose of ascorbate.

**j** In case of radiation treatment delays due to holidays

**k**  $\pm 7$  days prior to day 1

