## 12. STATISTICAL CONSIDERATIONS

### 12.1 Phase Ib

The primary objective of the Phase Ib portion of this study is to confirm the current standard dose of intravenous ascorbate, 75 gm, utilized in patients diagnosed with pancreatic cancer also receiving concurrent chemo radiation is safe within this population of sarcoma patients being treated concurrently with pre-operative radiation. Up to six (6) patients will be recruited to the standard dose, 75 grams administered intravenously 3 times a week during radiation therapy (5 weeks). If at most 1 out of 6 patients experience a DLT, the standard dose will be considered safe. If 2 or more patients experience a DLT, the next cohort of patients will be assigned to dose level - 1. The recommended phase II dose (RP2D) will be defined as the highest dose level for which at most 1 out of 6 patients experience a DLT.

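### Section 5.3 plans 15 ascorbate doses and also dosing to the end of radiation; the 28-fraction retroperitoneal course cannot satisfy both, since it yields 16 to 18 infusions

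*Combined protocol and SAP*

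**What the plan says.** Section 5.3 (Phase 2) starts ascorbate with radiation: "patients will receive the first dose of pharmacological ascorbate intravenously on day 1 of week 1". It continues: "This will be followed by 3 times a week dosing (= 15 doses total) at Dose 0 until completion of EBRT". The same paragraph sets the radiation course by site: "50 Gy over 25 fractions for extremity and trunk sarcoma or 45 to 50.4 Gy in 28 fractions for retroperitoneal sarcomas". It makes no exception to the dose count for retroperitoneal patients.

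Other sections fall into two groups.

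- **To the end of radiation.** Section 5.6.5: "Subjects will continue with therapy until the end of standard radiation therapy", unless a removal criterion is met. Sections 5.2 and 5.7 give the same stopping point, and Section 5.7 repeats that "those with retroperitoneal STS will receive 45 to 50.4 Gy in 28 fractions".
- **Five weeks.** Section 12.1 describes dosing "3 times a week during radiation therapy (5 weeks". The calendar in Section 10.1 marks three infusions in each of weeks 1 to 5. It allows one further week, which footnote j explains as "In case of radiation treatment delays due to holidays".

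On sampling, Section 9.4 places the final ascorbate level "30 min post last infusion in week 5", and calendar footnote f does the same. The table in Section 9.1 instead ties that level to the last ascorbate dose and the ROS sample to the last radiation fraction, but puts both in a row labelled W5.

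**The concern.** Fifteen is three times five, so the figure looks as if it was worked out for a five-week course and then applied to every patient. Retroperitoneal sarcoma is a named site in the objectives, the eligibility criteria and Section 5.3 itself. For a patient on 28 fractions, site staff must either stop at 15 and leave the last part of radiation uncovered, or go on to the end of radiation and exceed the stated total. Each choice breaks a written rule, and Appendix D requires deviations to be documented and monitors to check compliance with the study plan.

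What is at stake is the planned exposure of one tumour-site subgroup and the timing of a few end-of-treatment measurements. If patients are handled differently, the treatment whose pCR rate is reported will not be the one the protocol describes for that subgroup.

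**Working it through.** **Inputs**

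- Infusions: three a week, the first on week 1 day 1 (Section 5.3). The 15 g screening test dose is not counted.
- Fractions: 25 for extremity and trunk, 28 for retroperitoneal (Sections 5.2, 5.3 and 5.7).
- Dose per infusion: 75 g (Dose 0).
- Assumption: five weekday fractions a week, uninterrupted. The protocol does not state a weekly number. Section 5.7.5 says daily for the 25-fraction course, and 25 fractions at five a week fit the five weeks in Section 12.1.

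**Step 1: reproduce the stated figure.** 25 / 5 = 5 full weeks, and 5 × 3 = 15 infusions. This holds whichever three weekdays are used, so the stated 15 is right for every 25-fraction course. That includes the 25-fraction integrated-boost course allowed in select retroperitoneal cases.

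**Step 2: length of the 28-fraction course.** 28 / 5 = 5.6 weeks, that is 5 full weeks plus 3 treatment days. The last fraction falls on day 3 of week 6.

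**Step 3: infusions through the last fraction.** The five full weeks give 15. Week 6 adds the infusions that fall on its first three treatment days. Day 1 is always an infusion day, because the weekly pattern starts with an infusion on fraction 1. The other two infusion days are chosen from days 2 to 5, which gives six weekly patterns:

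| Other two infusion days | Patterns | Added in week 6 | Total |
|---|---|---|---|
| Both on days 4 and 5 | 1 of 6 | 1 | 16 |
| One on day 2 or 3, one on day 4 or 5 | 4 of 6 | 2 | 17 |
| Both on days 2 and 3 | 1 of 6 | 3 | 18 |

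Enumerating every infusion-day pattern with every possible starting weekday (30 combinations) gives the same split: 16 in 5, 17 in 20, 18 in 5, and 15 in none. Monday/Wednesday/Friday gives 17 whichever of those days treatment starts on.

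**Step 4: cumulative dose**

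- 15 × 75 = 1,125 g (stated total)
- 16 × 75 = 1,200 g (+75 / 1,125 = +7%)
- 17 × 75 = 1,275 g (+150 / 1,125 = +13%)
- 18 × 75 = 1,350 g (+225 / 1,125 = +20%)

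**Step 5: timing of samples in a 28-fraction patient**

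- *If dosing runs to the end of radiation:* the last infusion of week 5 is followed by 1 to 3 more. The level in Section 9.4 and footnote f is then not the post-last-dose level in the Section 9.1 table. The calendar's last CBC (week 5) also precedes those infusions. The CMP is taken in week 5 and again at the off-treatment visit.
- *If dosing stops at 15:* the last infusion is in week 5 and the last fraction in week 6. The W5 row of the Section 9.1 table no longer describes one time point, and the two draw times it permits for the immunology sample fall in different weeks.

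**The case against.** The strongest reply is that the 15 is a single parenthesis in Section 5.3, that three other sections give the end-of-radiation rule, and that staff would follow it. The affected group is also limited: extremity, trunk and 25-fraction boost patients all receive exactly 15, and the number of 28-fraction patients is not stated. The limits on scope stand. But the 15 is not isolated, because Section 12.1 and the calendar grid also assume five weeks, and the calendar's extra week is for holiday delays, not for a longer planned course.

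Several stronger conclusions might be inferred, and the documents do not support them.

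- *That the recommended Phase 2 dose becomes unclear.* Section 12.1 defines it by dose level, and a dose level is grams per infusion three times weekly. No cumulative count enters. A patient given 15 infusions of 75 g and one given 17 are at the same dose level.
- *That the DLT assessment is undermined.* The 15-dose figure appears only in Section 5.3. Section 5.2, which governs Phase Ib, gives no count. Section 6.3 refers to treatment and to 28 days after the first infusion. If the 28 days close the window, week 6 lies outside it, since it begins 35 days after a week 1 day 1 start.
- *That the last infusions follow all safety monitoring.* The calendar repeats the CMP, vital signs and adverse-event review at the off-treatment visit, 4 to 6 weeks after the last ascorbate dose, and blood pressure is tied to the infusions. Only the CBC ends at week 5.
- *That end-of-treatment sampling is mistimed throughout.* The Section 9.1 table already ties the ascorbate level and the ROS draw to events. What needs correcting is the week 5 wording in Section 9.4 and footnote f, and the W5 label. The stated purpose of the levels, confirming that a 20 mM target is reached, is served about as well by a week 5 sample.
- *That stopping at 15 uniquely leaves fractions without ascorbate.* With three infusions a week, 28 − 17 = 11 fractions have no same-day infusion even on the longer Monday/Wednesday/Friday schedule.

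**Conclusion.** The contradiction is real and confined to patients on the 28-fraction retroperitoneal course. For them the total of 15 and dosing to the completion of radiation cannot both be met: the gap is 1 to 3 infusions, 75 to 225 g at 75 g each, and most often 2 infusions (150 g, 13%). This rests on five uninterrupted weekday fractions a week and a fixed weekly infusion pattern starting on fraction 1. A secondary inconsistency follows for the final ascorbate level and, if dosing runs to the end of radiation, for the last CBC.

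The RP2D definition, the sample of 25, the rule of 6 or more responders and the stated power do not depend on the infusion count and are unaffected. The documents do not settle which rule was intended, and this review takes no position on that. The point merits correction because a stated treatment figure is wrong for a named tumour site and the repair is cheap.

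**What to change.** Reconcile Sections 5.3, 5.6.5, 9.1, 9.4, 10.1 and 12.1, and check the result against Sections 5.2 and 5.7.

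- State the planned number of infusions separately for the 25-fraction and 28-fraction courses. The sponsor decides which rule is intended for the latter.
- Bring the five-week statement in Section 12.1 and the calendar columns into line with that decision, so that a planned sixth week, if there is one, is distinct from the allowance for holiday delays.
- In Section 9.4, calendar footnote f and the calendar's week 5 labs, replace the week 5 anchor with the actual last infusion or last fraction, consistent with the events named in the Section 9.1 table. Relabel that table's W5 row, and say which event governs the immunology sample when the two fall in different weeks.

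The cost is an amendment to protocol and calendar wording. No extra samples or patients are needed, and the statistical design does not change.

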## 5.4 Study Timeline Schema:

## Phase 1b schema:

## Phase 2 schema:

## 5.5 Post-consent Screening Procedures

If subjects fail the G6PD or test doses of ascorbate, they are considered a screen failure.

- G6PD test (off-site test, so draw immediately). If subject has a prior G6PD test, this can be used as G6PD levels do not fluctuate (i.e., there is no window for this test).
- One test dose of 15g of ascorbate. A physician must review the patient's medication list against the list of medications prohibited on this trial prior to the test dose of ascorbate.

## 5.6 Concomitant Ascorbate (High-dose Ascorbic Acid) Infusions

5.6.1 **Participant dose.** All patients will receive a standard ascorbate dose of 75 gm given over 120 minutes

5.6.2 **Administration.** Based on subject tolerance; infusion rate should not exceed 500 mL/hour without consulting with physician. Recommended infusions times are as follows (Table 1) but may be adjusted for subject comfort. Changes in infusion rates should be recorded.

5.6.3 **Initiation.** Start the week prior to chemoradiation with one 15-g infusion. This is the test dose. 75 gm dosing begins week 1 of radiation therapy. If the participant fails the 15g test dose it is not considered dose limiting toxicity.

5.6.4 **Schedule.** Scheduled three times weekly during chemoradiation;

5.6.5 **Duration.** Subjects will continue with therapy until the end of standard radiation therapy or if any criteria of removal are met (Section 5.7)

5.6.6 **Dose modifications.** Provided in Section 6.2

**Table 1.** Recommended Infusion Times for Pharmacological Ascorbate †

Ascorbate dose (500 mg / mL)	Total volume*	Osmolarity (mOsm/L) §	Infusion Time
15g (30 mL)	250 mL	681	30 minutes
75g (150 mL)	1000 mL	851.7	120 minutes
62.5 g (125 mL)	1000 mL	709	120 mins

† Provided by Drug Information Center at the University of Iowa, July 2011

\* Sterile water for injection only. Do not use D5W

§ Theoretical calculations provided by Drug Information Center; targeted osmolarity range is 500 – 900 mOsm/L

## 5.7 Radiation therapy

External beam radiation therapy will be given at the standard dose for resectable soft tissue sarcomas according to the NCCN sarcoma guidelines. Patients with extremity and trunk STS will receive 50 Gy over 25 fractions and those with retroperitoneal STS will receive 45 to 50.4 Gy in 28 fractions, during which time they will be receiving three times weekly IV ascorbate until the end of radiation therapy. Surgery will be performed 4-6 weeks from the end of radiation to allow for adequate tissue healing and resolution of acute toxicities.

Radiation therapy for this protocol is as per currently used standard pre-operative radiation therapy at the University of Iowa even for non-protocol patients. Selected guidelines from previously conducted Radiation Therapy Oncology Groups (RTOG) studies are briefly summarized for this protocol.

- 5.7.1 **Preoperative Radiation therapy (3D-CRT or IMRT).** Either 3D conformal radiotherapy or intensity modulated radiation therapy may be utilized for adequate tumor coverage and to meet the dose constraints for critical normal structures.
- 5.7.2 **Radiation treatment planning scans and immobilization.** CT scans with patient in a stable and comfortable position will be used for planning. MRI scans are optional and may be used for co-registration with CT for tumor localization as needed. VacLoc or other immobilization devices can be used for immobilization.
- 5.7.3 **Target volumes and treatment field (Extremity Sarcoma):**

**Gross Target Volume (GTV):** Outline of the tumor as seen on CT or CT/MRI fusion.

**Clinical Target Volume (CTV):** CTV = GTV plus 4 cm margins in the proximal and distal directions. However, the margin can be reduced if it extends beyond the compartment, the field can be shortened to include the end of a compartment. The radial margin from the lesion should be 1 cm. It can be reduced in areas confined by the fascial barrier or bone or skin surface as per standard of care and treating radiation oncologist's discretion.

**Planning Target Volume (PTV):** Include CTV and error of setup and organ motion. Typically PTV includes CTV plus 0.5 - 1 cm in all dimensions. Final PTV is usually GTV + 5 cm longitudinal and 2 cm radial, except where restricted by the compartment end, fascia, bone or skin surface as per standard of care and treating radiation oncologist's discretion.

Use of bolus on the skin surfaces is optional as needed. Where applicable biopsy scars should be bolused with appropriate thickness specific to the energy of the photon beam.

- 5.7.4 **Target volumes and treatment field (Retroperitoneal/Trunk Sarcoma):**

**Gross Target Volume (GTV):** Outline of the tumor as seen on CT or CT/MRI fusion.

**Clinical Target Volume (CTV):** 4D-CT imaging should be performed for tumors above the iliac brim to assess for possible tumor motion associated with respiration. The CTV is generated by expanding the different respiratory phases GTV (ITV) by 1.5 cm symmetrically. The margin can be reduced if it extends beyond the retroperitoneal compartment into bone, kidney, or liver. If tumor extends through inguinal canal, an additional 3cm can be added distally as per standard of care and treating radiation oncologist's discretion.

**Planning Target Volume (PTV):** Include CTV and error of setup and organ motion. PTV expansions are typically CTV plus 0.5 - 1 cm in all dimensions. Final PTV is typically ITV + 2 cm symmetrically as confined to the retroperitoneal compartment as per standard of care and treating radiation oncologist's discretion.

